2. Ensure the overall systolic blood pressure is within the range of ≤ 100 to ≥ 170 mmHg and the overall diastolic blood pressure is within the range of ≤ 50 to ≥ 120 mmHg.
3. If the participants have a blood pressure outside the range of 90–180mmHg for systolic blood pressure and 40–130mmHg for diastolic blood pressure, only a maximum of 4 blood pressures readings outside of this range can be included in the analysis.
4. Ensure there are approximately 26-31 participants in each of the 3 blood pressure ranges (low blood pressure (systolic: 0-129, diastolic: 0-79), medium blood pressure (systolic: 130-160, diastolic: 80-100) and high blood pressure (systolic: 161 or higher, diastolic: 101 or higher)).

Data Analysis

[figure not shown]
The profile of the study participants will be described based on a demographic analysis conducted on data collected from the subject data form from the ESH-IP (**Appendix M**).

All collected data on Forms 1 and 2 will be sent to the researchers at the SE Research Centre, who will consolidate the data from the Forms 1 and 2 and analyze the data as specified in Form 3, the Study Results form from the ESH-IP (**Appendix N**) (O'Brien et al., 2010).

In order to pass the validation process, the device must pass both parts 1 and 2 based on the accuracy criteria table (**Appendix O**).

Plots

These are mean-difference plots, and the plots modelled from the data collected should be exactly as shown in the example plots below.

The x-axis of these plots represents blood pressures in the systolic range 80mmHg–190mmHg and the diastolic range 30 mmHg–140 mmHg. The y-axes represent errors from – 30mmHg to +30mmHg. Horizontal reference lines will be drawn at 5mmHg intervals from +15mmHg to – 15 mmHg. The mean of each device pressure and its corresponding observer pressure will be plotted against their difference with a point. Differences greater than 30mmHg will be plotted at 30 mmHg. Differences less than – 30mmHg will be plotted at – 30 mmHg. The same scales will be used for both SBP and DBP plots. Where points are superimposed, these will be indicated either by proportionately larger points or by different symbols.

5. Confidentiality and security of data

Electronic data

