- ☞ If possible, a permanent record of device measurements should be kept. If software is provided, device measurements should be downloaded daily.

Recruitment details

Date and time	201	Study number and Subject number	202	203
Date of birth	204	Age	205	
Sex	Male 206	On antihypertensive medication	Yes 207	No 207
Arm circumference cm	208	Cuff for test device	Standard 209	Other 209
Wrist circumference cm	210	Height ft, in		Weight lbs

Box 209: This is only required for arm devices. If the arm circumference is such that no suitable cuff is available, circle *Cuff size unavailable* in Box 287 and exclude the subject.

Box 210: This is only required for wrist devices.

Entry measurements

Ask the subject to relax for 10–15 min. Then make sure that the subject is seated with legs uncrossed and back supported. Ensure that the arm is supported at heart level. If a wrist device is being tested, the wrist must be supported according to the manufacturer's instructions. If the subject is not seated as described, the posture used must be recorded as a protocol adjustment.

BPA	Observer 1		Observer 2		Device		Heart Rate bpm	
	SBP	DBP	SBP	DBP	SBP	DBP		
	211	212		213	214		215	216
	Observer Mean			Category			Count	
BPA	SBP	DBP	SBP	DBP	SBP	DBP		
	217	218	LL L M H HH 219	LL L M H HH 220	221	222		

Boxes 217, 218: Enter the rounded up averages of Boxes 211 and 213 and of Boxes 212 and 214 respectively.

Box 219: Circle the range according to the BP in Box 217. LL: < 90, L: 90–129, M: 130–160, H: 161–180, HH: >180.

Box 220: Circle the range according to the BP in Box 218. LL: < 40, L: 40–79, M: 80–100, H: 101–130, HH: >130.

Boxes 221, 222: Update the running totals, for the ranges (counting LL and L together and counting HH and H together) in Boxes 219 and 220, and enter them respectively.

- ☞ If both Box 221 and Box 222 are greater than 12 or if an *LL* or *HH* is circled and there are already 4 such items circled, circle *Ranges complete* in Box 287 and exclude the subject.

- ☞ If one of Box 221 or Box 222 is greater than 12 but the other is not, it may be necessary to include this subject, and remove another, in order to achieve the correct range distribution; in the removed subject, circle *Range adjustment* in Box 287.

Validation measurements

	BP1		BP3		BP5		BP7	
	SBP	DBP	SBP	DBP	SBP	DBP	SBP	DBP
Observer 1	223	224	225	226	227	228	229	230
Observer 2	231	232	233	234	235	236	237	238
Observer mean	239	240	241	242	243	244	245	246

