Box 308: The number of subjects excluded with *Cuff size availability* circled in *Box 287*.

Box 309: The number of subjects excluded with *Observer disagreement* circled in *Box 287*.

Box 310: The number of subjects excluded with *Distribution* circled in *Box 287*.

Box 311: The number of subjects excluded with *Other reasons* circled in *Box 287*. A summary of those reasons must be provided in Box 313.

Box 312: The total recruited equals the number screened (Box 301) less the number excluded (Box 302). This should equal 33 except in validations in some specific populations.

Box 313: A summary of why those counted in Box 311 were excluded (*Box 288*).

Boxes 314–323: In a completed study in a general adult population, the sum of Boxes 314 and 315, Box 316, the sum of Boxes 317 and 318, the sum of Boxes 319 and 320, Box 321 and the sum of Boxes 322 and 323 must each be between 10 and 12. The sum of Boxes 314, 318, 319 and 323 must be at most 4. The sum of Boxes 314–318 and the sum of Boxes 319–323 must each be exactly 33. Studies in specific populations may have different restrictions and totals (*Boxes 219 and 220 – Form 2 for each included subject*).

Boxes 324–329: The number of subjects in each range on antihypertensive medication (*Boxes 207, 219 and 220*).

Table 2 Subject details

Sex	Male : Female	330	
Age (years)	Range (Low : High)	331	
	Mean (SD)	332	
Arm circumference (cm)	Range (Low : High)	333	
	Mean (SD)	334	
Cuff for test device (Upper arm devices only)	Small	335	— — cm
	Standard	336	— — cm
	Large	337	— — cm
	Other	338	— — cm
Wrist circumference (cm) (Wrist devices only)	Range (Low : High)	339	
	Mean (SD)	340	
Recruitment BP (mmHg)	Range (Low : High)	341	SBP
		342	DBP
	Mean (SD)	343	
		344	

Note: The values in Boxes 314–380 refer only to the final recruited subjects, each of whom contributes SBP and DBP measurements for analysis. Excluded subjects are not included in any of this analysis.

Box 330: Enter the number of males, a colon and the number of females. They should total 33 except in validations in some specific populations. If the minimum requirements (10 for a general population) are not met, subjects must be replaced as necessary (Box 206).

Box 331: Enter the age of the youngest subject, a colon and the age of the oldest subject e.g. 31:74. Subjects outside the required range (25 and over for a general population) are not permitted (Box 205).

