Boxes 346–348: The observer measurements (three per subject) for SBP are categorised similarly to the recruitment ranges. Enter the counts of measurements falling into each range. These must total 99 (Boxes 281, 283 and 285).

Box 349: Subtract the smallest value from Boxes 346 to 348 from the largest one and enter the result.

Box 350: Enter the lowest pressure, a colon and the highest DBP from the observer measurements (Boxes 282, 284 and 286).

Boxes 351–353: The observer measurements (three per subject) for DBP are categorised similarly to the recruitment ranges. Enter the counts of measurements falling into each range. These must total 99 (Boxes 282, 284 and 286).

Box 354: Subtract the smallest value from Boxes 351 to 353 from the largest one and enter the result.

- In order to ensure a uniform distribution, there must be at least 22 measurements and at most 44 measurements (Boxes 346 to 348 and 351 to 353) in each of the low, medium and high ranges and the maximum differences (Boxes 349 and 354) must be at most 19. If not, further recruitment will be necessary. Subjects to be excluded will be those whose pressures drifted from recruitment pressures.
- The overall SBP range must be from ≤ 100 mmHg to ≥ 170 mmHg and the overall DBP range must be from ≤ 50 mmHg to ≥ 120 mmHg. If not, further recruitment will be necessary. Subjects to be excluded will be the last recruited within the relevant ranges.
- The minimum number of replacements should take place. If a subject is replaced for either of these reasons, circle *Distribution* in *Box 287 of Form 2* for that subject.
- In validations carried out in specific populations requiring more than 33 subjects but with similar blood pressure distributions, similar proportions should be used. If the blood pressure distribution in the specific population differs from the standard distribution, ignore this table but comment on the distribution in the discussion.

Table 4 Observer differences

This section is for the differences in pressures between the two observers

Observer 2–Observer 1	SBP	DBP	Repeated measurements
	Range (Low : High)	355	356
	Mean (SD)	357	358

Boxes 355–356: Enter the lowest difference, a colon and the highest difference between the observers. Include the signs e.g. $-3:+4$. (Boxes 247, 249, 251 and 253 and Boxes 248, 250, 252 and 254). If the range is outside $-4:+4$, then this is a violation. Relevant subjects should be excluded, by reason of Observer Disagreement, and replaced.

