Appendix O – International Protocol Accuracy Criteria

ESH International Protocol 2010			
Sequential Measurements			
IP Grading Part 1 - Minimum Requirements (at least 255 pairs of individual measurements)			
N	≤ 5 mmHg	≤ 10 mmHg	≤ 15 mmHg
Two of	188	224	247
All of	167	209	240
IP Grading Part 2 (85 subject mean pressures)			
N	$2/3 \leq 5$ mmHg		$0/3 \leq 5$ mmHg
At least	62		
At most			8
Recruitment Ranges (n = 85)			
SBP		DBP	
mmHg	Subjects	mmHg	Subjects
90*...129	26 – 31	40*...79	26 – 31
130...160	26 – 31	80...100	26 – 31
161...180*	26 – 31	101...130*	26 – 31
*	Altogether, up to 4 recruitment pressures are permitted to be outside these limits.		
Test Measurement Distribution			
SBP		DBP	
mmHg	Measurements	mmHg	Measurements
≤ 100	≥ 3	≤ 50	≥ 3
< 130	57 – 113*	< 80	57 – 113*
130...160	57 – 113*	80...100	57 – 113*
> 160	57 – 113*	> 100	57 – 113*
≥ 170	≥ 3	≥ 120	≥ 3
*	The difference between the maximum and minimum of these 3 counts for SBP and, separately, for DBP, must be less than or equal to 19.

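### Data Checking item 3 caps at 4 the out-of-limit readings that may be analysed, whereas Forms 2 and 3 and Appendix O apply the same cap to recruitment pressures; the cap must name one unit

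*Combined protocol and SAP*

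**What the plan says.** The protocol body (section 3, Data Checking, item 3) deals with pressures outside 90–180 mmHg SBP or 40–130 mmHg DBP and states that "only a maximum of 4 blood pressures readings outside of this range can be included in the analysis".

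Three other places use the same limits and the same number, but count something else:

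- **Form 2, Entry measurements.** The LL and HH categories come from the entry measurement BPA: "Box 219: Circle the range according to the BP in Box 217", and Box 220 does the same for DBP from Box 218. A subject is excluded when an LL or HH "is circled and there are already 4 such items circled".
- **Form 3, Boxes 314–323.** These boxes hold the recruitment-range counts, and "The sum of Boxes 314, 318, 319 and 323 must be at most 4". Boxes 314 and 318 are the outer SBP ranges; 319 and 323 are the outer DBP ranges.
- **Appendix O, Recruitment Ranges.** "Altogether, up to 4 recruitment pressures are permitted to be outside these limits".

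The accuracy analysis uses other data, namely the test readings, three per subject for each component: "Boxes 346–348: The observer measurements (three per subject) for SBP are categorised similarly to the recruitment ranges". Appendix O sets its Part 1 marks for "at least 255 pairs of individual measurements" and its Part 2 marks for 85 subjects.

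**The concern.** One rule appears with two different units. In the forms and Appendix O it limits who is recruited, and every included subject then contributes all three test readings. In Data Checking item 3 it limits which readings are analysed.

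If item 3 were followed literally, three things could go wrong:

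1. Test pairs would be kept or dropped according to their observed value, at the extremes of pressure. Item 3 does not say which four to keep, nor whether the observer's or the device's value decides.
2. A subject who loses a reading would no longer have the three differences on which Part 2 is defined, and no rule says how to grade that subject.
3. The Part 1 marks are absolute counts. With fewer pairs, the same counts demand a higher proportion.

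At stake is which data enter a pass/fail decision that is meant to support applications to Health Canada and the FDA.

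**Working it through.** **Step 1: reproduce the Appendix O marks.** Form 3 gives marks for 33 subjects (99 pairs) and asks for proportional scaling in larger studies. With 85 subjects there are 3 × 85 = 255 pairs.

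- Part 1, two of: 73, 87, 96 × 255/99 = 188.0, 224.1, 247.3. Appendix O has 188, 224, 247.
- Part 1, all of: 65, 81, 93 × 255/99 = 167.4, 208.6, 239.5. Appendix O has 167, 209, 240.
- Part 2: 24 and 3 × 85/33 = 61.8 and 7.7. Appendix O has 62 and 8.

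All match, so the marks are tied to 255 pairs and 85 subjects.

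**Step 2: compare the units.**

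| Place | What is counted | Cap |
|---|---|---|
| Data Checking item 3 | readings entering the analysis | 4 |
| Form 2, Boxes 217–220 | LL/HH categories of BPA | 4 |
| Form 3, Boxes 314, 318, 319, 323 | recruitment pressures, SBP plus DBP | 4 |
| Appendix O | recruitment pressures, SBP and DBP together | 4 |

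BPA is not one of the readings compared with the device for accuracy; those come from BP1 to BP7. A cap on BPA therefore removes no test pair, while a cap on analysed readings can.

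**Step 3: look for a route that absorbs a removal.** Box 287 has no exclusion reason for a test reading outside these limits. Form 2 notes that subjects may be excluded later because their pressure changed, but it refers to Form 3, where the Distribution replacement covers only the low/medium/high counts and the overall range. Neither Form 3 Table 3 nor Appendix O's test measurement distribution caps readings beyond 90–180 or 40–130 mmHg.

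**Step 4: worst case without drift in other subjects.** Assumptions: exactly 85 subjects; all 4 permitted out-of-limit recruitment pressures in one component (all SBP or all DBP); every test reading of those pressures stays outside; item 3 applied reading by reading.

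- Readings outside: 4 × 3 = 12
- Dropped: 12 − 4 = 8
- Pairs left: 255 − 8 = 247

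| Mark | Intended, of 255 | Required, of 247 |
|---|---|---|
| Two of: 188 within 5 mmHg | 73.7% | 76.1% |
| Two of: 224 within 10 mmHg | 87.8% | 90.7% |
| Two of: 247 within 15 mmHg | 96.9% | 100% |
| All of: 167 within 5 mmHg | 65.5% | 67.6% |
| All of: 209 within 10 mmHg | 82.0% | 84.6% |
| All of: 240 within 15 mmHg | 94.1% | 97.2% |

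The first line of marks needs only two of its three counts, so the 100% requirement alone does not fail the device.

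**Step 5: range.** Under the same assumptions, but letting test readings fall back inside the limits, between 0 and 8 readings are dropped. If the four pressures are split two and two between SBP and DBP, and the eight removals fall evenly, each component loses 4. Then 255 − 4 = 251 pairs remain, and the 15 mmHg marks need 247/251 = 98.4% and 240/251 = 95.6%. Losing more than 8 requires out-of-limit readings from other subjects. From 9 dropped (246 left) the 247 mark cannot be reached. From 16 dropped (239 left) the mandatory 240 mark cannot be reached, and the device fails whatever its accuracy.

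**Step 6: with the cap on recruitment pressures.** No test pair is dropped, 255 pairs and 85 subjects stand, and every Appendix O mark keeps its intended proportion.

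**The case against.** The best reply is that item 3 is only a loose restatement of the recruitment rule. It begins with participants whose pressure lies outside the limits, sits in a list of daily checks during data collection, and precedes a recruitment quota. Form 3 leaves excluded subjects out of the analysis, so a fifth LL or HH subject, excluded under Form 2, would indeed not be analysed. The protocol says it follows the ESH-IP precisely apart from the consensus modification, and that the analysis follows Form 3, which takes three measurements per subject. No form describes deleting a single reading. If whole subjects were excluded instead, recruitment continues until at least 85 complete, and 255 pairs would be preserved.

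Much of this stands. It probably explains how the sentence arose, and it makes the harm conditional on a literal reading. It does not cure the text. Item 3 speaks of readings in the analysis, BPA pressures are not in the accuracy analysis, and no form excludes or replaces a subject because a test reading lies outside these limits.

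Two stronger readings are tempting and are not supported:

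- **That the cap will usually or always be exceeded, so that valid readings are bound to be lost.** This depends on how pressures spread within the high range, on drift after entry and on rounding. The documents do not give these, and they expect some pressures to drift from the recruitment value.
- **That the rule could let an inaccurate device pass Part 1.** Removing pairs against fixed counts can only lower the numbers within 5, 10 and 15 mmHg. It cannot turn a Part 1 fail into a pass. In Part 2 no direction can be claimed, because grading with fewer than three differences is undefined.

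**Conclusion.** The inconsistency holds. Data Checking item 3 and the three operative texts (Form 2, Form 3 and Appendix O) share limits and number but not the unit counted, and the body text, read as written, tells researchers to restrict the analysed data. The contradiction needs no calculation.

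Its consequence is conditional: it arises only if item 3 is applied literally and more than 4 test readings fall outside the limits. The worst case in Step 4 is a bound under its stated assumptions, not an expected result. In Part 1 the harm is a test stricter than intended; in Part 2 it is a missing grading rule for affected subjects. A reader might also infer that pairs will be dropped as a matter of course, but the documents support only that they could be.

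Severity: moderate. It should be corrected before analysis, so that which pairs count is not decided after the readings have been seen.

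**What to change.** Reword Data Checking item 3 so that it names the same unit as Forms 2 and 3 and Appendix O. Suggested text: *At most 4 recruitment pressures (BPA, Boxes 217 and 218, SBP and DBP together) may lie outside 90–180 mmHg SBP or 40–130 mmHg DBP; all three test readings of every included subject stay in the analysis.*

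Forms 2 and 3 and Appendix O need no change on this point. The cost is one sentence in the protocol, with no further data or participants.

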- ☞ If possible, a permanent record of device measurements should be kept. If software is provided, device measurements should be downloaded daily.

Recruitment details

Date and time	201	Study number and Subject number	202	203
Date of birth	204	Age	205	
Sex	Male 206	On antihypertensive medication	Yes 207	No 207
Arm circumference cm	208	Cuff for test device	Standard 209	Other 209
Wrist circumference cm	210	Height ft, in		Weight lbs

Box 209: This is only required for arm devices. If the arm circumference is such that no suitable cuff is available, circle *Cuff size unavailable* in Box 287 and exclude the subject.

Box 210: This is only required for wrist devices.

Entry measurements

Ask the subject to relax for 10–15 min. Then make sure that the subject is seated with legs uncrossed and back supported. Ensure that the arm is supported at heart level. If a wrist device is being tested, the wrist must be supported according to the manufacturer's instructions. If the subject is not seated as described, the posture used must be recorded as a protocol adjustment.

BPA	Observer 1		Observer 2		Device		Heart Rate bpm	
	SBP	DBP	SBP	DBP	SBP	DBP		
	211	212		213	214		215	216
	Observer Mean			Category			Count	
BPA	SBP	DBP	SBP	DBP	SBP	DBP		
	217	218	LL L M H HH 219	LL L M H HH 220	221	222		

Boxes 217, 218: Enter the rounded up averages of Boxes 211 and 213 and of Boxes 212 and 214 respectively.

Box 219: Circle the range according to the BP in Box 217. LL: < 90, L: 90–129, M: 130–160, H: 161–180, HH: >180.

Box 220: Circle the range according to the BP in Box 218. LL: < 40, L: 40–79, M: 80–100, H: 101–130, HH: >130.

Boxes 221, 222: Update the running totals, for the ranges (counting LL and L together and counting HH and H together) in Boxes 219 and 220, and enter them respectively.

- ☞ If both Box 221 and Box 222 are greater than 12 or if an *LL* or *HH* is circled and there are already 4 such items circled, circle *Ranges complete* in Box 287 and exclude the subject.

- ☞ If one of Box 221 or Box 222 is greater than 12 but the other is not, it may be necessary to include this subject, and remove another, in order to achieve the correct range distribution; in the removed subject, circle *Range adjustment* in Box 287.

Validation measurements

	BP1		BP3		BP5		BP7	
	SBP	DBP	SBP	DBP	SBP	DBP	SBP	DBP
Observer 1	223	224	225	226	227	228	229	230
Observer 2	231	232	233	234	235	236	237	238
Observer mean	239	240	241	242	243	244	245	246
Observer difference	247	248	249	250	251	252	253	254
	BP2		BP4		BP6		Difference	
	SBP	DBP	SBP	DBP	SBP	DBP	A	0–5 mmHg
Device	255	256	257	258	259	260	B	6–10 mmHg
Device–Previous observer	261	262	263	264	265	266	C	11–15 mmHg
Device–Next observer	267	268	269	270	271	272	D	> 15 mmHg
Error group	A B C D 273	A B C D 274	A B C D 275	A B C D 276	A B C D 277	A B C D 278	Within 5 mmHg	
Observer value	281	282	283	284	285	286	SBP	DBP

Boxes 239–246: Enter the rounded up averages of Boxes 223 and 231, of Boxes 224 and 232, of Boxes 225 and 233, of Boxes 226 and 234, of Boxes 227 and 235, of Boxes 228 and 236, of Boxes 229 and 237 and of Boxes 230 and 238 respectively.

Boxes 247–254: Enter the differences Box 223–Box 231, Box 224–Box 232, Box 225–Box 233, Box 226–Box 234, Box 227–Box 235, Box 228–Box 236, Box 229–Box 237, and Box 230–Box 238 respectively.

Boxes 261–266: Enter the 'Device–Previous Observer Mean' differences. These are Box 255–Box 239, Box 256–Box 240, Box 257–Box 241, Box 258–Box 242, Box 259–Box 243, and Box 260–Box 244 respectively.

Boxes 267–272: Enter the 'Device–Next Observer Mean' differences. These are Box 255–Box 241, Box 256–Box 242, Box 257–Box 243, Box 258–Box 244, Box 259–Box 245, and Box 260–Box 246 respectively.

Each device measurement is compared to the nearer of the previous and next observer measurement. As described below, the smaller error is circled and the corresponding observer measurement is copied to aid the analysis.

Box 273: First, circle the smaller value, in absolute terms, of Boxes 261 and 267 (Box 261 if both are the same). Then circle A if this is less than or equal to 5, B if this is 6–10, C if this is 11–15 or D if this is greater than 15.

Boxes 274–278: Circle A, B, C or D, as described for Box 273, based on the smallest absolute values (also circled) of Boxes 261 and 268, Boxes 263 and 269, Boxes 264 and 270, Boxes 265 and 271 and Boxes 266 and 272 respectively.

Box 279: Enter the number of 'A's circled in Boxes 273, 275 and 277.

Box 280: Enter the number of 'A's circled in Boxes 274, 276 and 278.

The numbers of 'A's, 'B's and 'C's will be used in the analysis to calculate the number of device-observer differences within 5 mmHg, 10 mmHg and 15 mmHg.

Box 281: Enter the value in Box 239 if Box 261 is circled or Box 241 if Box 267 is circled.

Box 282: Enter the value in Box 240 if Box 262 is circled or Box 242 if Box 268 is circled.

Box 283: Enter the value in Box 241 if Box 263 is circled or Box 243 if Box 269 is circled.

Box 284: Enter the value in Box 242 if Box 264 is circled or Box 244 if Box 270 is circled.

Box 285: Enter the value in Box 243 if Box 265 is circled or Box 245 if Box 271 is circled.

Box 286: Enter the value in Box 244 if Box 266 is circled or Box 246 if Box 272 is circled.

Signoff

Please use the comments to explain unlisted subject exclusion or any problems during the procedure

Excluded	Ranges complete Poor quality sounds	Range adjustment Cuff size unavailable	Arrhythmias Observer disagreement	Device failure Distribution	Other	287
Comments						
	Supervisor signature					
	288					
	289					

Note: Subjects initially included may be excluded due to changes in pressure. See *observer measurements in each recruitment range in Form 3 – Study Results*.

If a printout of test device data is possible, print the device data for this subject and attach it to this form.

Form 3 – Study results

The data from *Form 2 – Subject Data* for each subject should be appropriately analysed so that the results on this form can be completed. All references to boxes 201–289 refer to values obtained from all of the Forms 2 from the relevant subjects. All blood pressure measurements are in mmHg.

Table 1 Screening and recruitment details

	Screening and recruitment	Recruitment ranges		
Total screened	301		mmHg	All
Total excluded	302		< 90	314
Ranges complete	303	Low	90–129	315
Range adjustment	304	SBP	130–160	316
Arrhythmias	305		161–180	317
Device failure	306	High	> 180	318
Poor quality sounds	307			
Cuff size unavailable	308	Low	< 40	319
Observer disagreement	309		40–79	320
Distribution	310	DBP	80–100	321
Other reasons*	311		101–130	322
Total recruited	312	High	> 130	323

*Explanation summary

313

Box 301: The total number of subjects screened, regardless of whether or not they were included in the study.

Box 302: The total number excluded. This equals the sum of Boxes 303–311.

Box 303: The number of subjects excluded with *Ranges complete* circled in *Box 287 (Form 2 for each excluded subject)*.

Box 304: The number of subjects excluded with *Range adjustment* circled in *Box 287*.

Box 305: The number of subjects excluded with *Arrhythmias* circled in *Box 287*.

Box 306: The number of subjects excluded with *Device failure* circled in *Box 287*.

Box 307: The number of subjects excluded with *Poor quality sounds* circled in *Box 287*.

Box 308: The number of subjects excluded with *Cuff size availability* circled in *Box 287*.

Box 309: The number of subjects excluded with *Observer disagreement* circled in *Box 287*.

Box 310: The number of subjects excluded with *Distribution* circled in *Box 287*.

Box 311: The number of subjects excluded with *Other reasons* circled in *Box 287*. A summary of those reasons must be provided in Box 313.

Box 312: The total recruited equals the number screened (Box 301) less the number excluded (Box 302). This should equal 33 except in validations in some specific populations.

Box 313: A summary of why those counted in Box 311 were excluded (*Box 288*).

Boxes 314–323: In a completed study in a general adult population, the sum of Boxes 314 and 315, Box 316, the sum of Boxes 317 and 318, the sum of Boxes 319 and 320, Box 321 and the sum of Boxes 322 and 323 must each be between 10 and 12. The sum of Boxes 314, 318, 319 and 323 must be at most 4. The sum of Boxes 314–318 and the sum of Boxes 319–323 must each be exactly 33. Studies in specific populations may have different restrictions and totals (*Boxes 219 and 220 – Form 2 for each included subject*).

Boxes 324–329: The number of subjects in each range on antihypertensive medication (*Boxes 207, 219 and 220*).

Table 2 Subject details

Sex	Male : Female	330	
Age (years)	Range (Low : High)	331	
	Mean (SD)	332	
Arm circumference (cm)	Range (Low : High)	333	
	Mean (SD)	334	
Cuff for test device (Upper arm devices only)	Small	335	— — cm
	Standard	336	— — cm
	Large	337	— — cm
	Other	338	— — cm
Wrist circumference (cm) (Wrist devices only)	Range (Low : High)	339	
	Mean (SD)	340	
Recruitment BP (mmHg)	Range (Low : High)	341	SBP
		342	DBP
	Mean (SD)	343	
		344	

Note: The values in Boxes 314–380 refer only to the final recruited subjects, each of whom contributes SBP and DBP measurements for analysis. Excluded subjects are not included in any of this analysis.

Box 330: Enter the number of males, a colon and the number of females. They should total 33 except in validations in some specific populations. If the minimum requirements (10 for a general population) are not met, subjects must be replaced as necessary (Box 206).

Box 331: Enter the age of the youngest subject, a colon and the age of the oldest subject e.g. 31:74. Subjects outside the required range (25 and over for a general population) are not permitted (Box 205).

Box 332: Enter the mean and, in parentheses, the SD of the subject ages. Values should be rounded up to one decimal place e.g. 52.3 (11.9) (Box 205).

Box 333: Enter the smallest arm circumference, a colon and the largest arm circumference e.g. 24:34 (Box 208).

Box 334: Enter the mean and, in parentheses, the SD of the subject arm circumferences. Values should be rounded up to one decimal place e.g. 29.0 (3.1) (Box 208).

Box 335: If a small cuff was supplied, enter the number of subjects on whom it was used. If it was not supplied, enter an 'X'. Enter the arm sizes for which it is recommended beside it. (Applicable only for arm devices) (Box 209).

Box 336: Enter the number of subjects on whom a standard (or medium) cuff was used. Enter the arm sizes for which it is recommended beside it. (Applicable only for arm devices) (Box 209).

Box 337: If a large cuff was supplied, enter the number of subjects on whom it was used. If it was not supplied, enter an 'X'. Enter the arm sizes for which it is recommended beside it. (Applicable only for arm devices) (Box 209).

Box 338: If a different size cuff was supplied, enter the number of subjects in whom it was used. If no such cuff was supplied, enter an 'X'. Enter the arm sizes for which it is recommended beside it. (Applicable only for arm devices) (Box 209).

Box 339: Enter the smallest wrist circumference, a colon and the largest wrist circumference e.g. 15:22 (Applicable only for wrist devices) (Box 210).

Box 340: Enter the mean and, in parentheses, the SD of the subject wrist circumferences. Values should be rounded up to one decimal place e.g. 18.1(2.3) (Applicable only for wrist devices) (Box 210).

Boxes 341–342: Enter the lowest pressure, a colon and the highest pressure from BPA measurements only e.g. 104:180. (Boxes 217 and 218).

Boxes 343–344: Enter the mean and, in parentheses, the SD of the subject pressures from BPA measurements only. Values should be rounded up to one decimal place e.g. 140.4 (20.3). (Boxes 217 and 218).

Table 3 Distribution

SBP	DBP
Overall range (Low : High)	Overall range (Low : High)
345	350
Low (<130)	Low (<80)
346	351
Medium (130–160)	Medium (80–100)
347	352
High (>160)	High (>100)
348	353
Maximum difference	Maximum difference
349	354

This section analyses the distribution of comparative measurements.

Box 345: Enter the lowest pressure, a colon and the highest SBP from the observer measurements (Boxes 281, 283 and 285).

Boxes 346–348: The observer measurements (three per subject) for SBP are categorised similarly to the recruitment ranges. Enter the counts of measurements falling into each range. These must total 99 (Boxes 281, 283 and 285).

Box 349: Subtract the smallest value from Boxes 346 to 348 from the largest one and enter the result.

Box 350: Enter the lowest pressure, a colon and the highest DBP from the observer measurements (Boxes 282, 284 and 286).

Boxes 351–353: The observer measurements (three per subject) for DBP are categorised similarly to the recruitment ranges. Enter the counts of measurements falling into each range. These must total 99 (Boxes 282, 284 and 286).

Box 354: Subtract the smallest value from Boxes 351 to 353 from the largest one and enter the result.

- In order to ensure a uniform distribution, there must be at least 22 measurements and at most 44 measurements (Boxes 346 to 348 and 351 to 353) in each of the low, medium and high ranges and the maximum differences (Boxes 349 and 354) must be at most 19. If not, further recruitment will be necessary. Subjects to be excluded will be those whose pressures drifted from recruitment pressures.
- The overall SBP range must be from ≤ 100 mmHg to ≥ 170 mmHg and the overall DBP range must be from ≤ 50 mmHg to ≥ 120 mmHg. If not, further recruitment will be necessary. Subjects to be excluded will be the last recruited within the relevant ranges.
- The minimum number of replacements should take place. If a subject is replaced for either of these reasons, circle *Distribution* in *Box 287 of Form 2* for that subject.
- In validations carried out in specific populations requiring more than 33 subjects but with similar blood pressure distributions, similar proportions should be used. If the blood pressure distribution in the specific population differs from the standard distribution, ignore this table but comment on the distribution in the discussion.

Table 4 Observer differences

This section is for the differences in pressures between the two observers

Observer 2–Observer 1	SBP	DBP	Repeated measurements
	Range (Low : High)	355	356
	Mean (SD)	357	358

Boxes 355–356: Enter the lowest difference, a colon and the highest difference between the observers. Include the signs e.g. $-3:+4$. (Boxes 247, 249, 251 and 253 and Boxes 248, 250, 252 and 254). If the range is outside $-4:+4$, then this is a violation. Relevant subjects should be excluded, by reason of Observer Disagreement, and replaced.

Boxes 357–358: Enter the mean and, in parentheses, the SD of the observer differences. Values should be rounded up to one decimal place e.g. 0.3 (1.2) (Boxes 247, 249, 251 and 253 and Boxes 248, 250, 252 and 254).

Boxes 359: Enter the number of measurements that were repeated in the included subjects because observers were more than 4 mmHg apart.

Table 5 Validation results

Part 1		$\leq 5\text{mmHg}$	$\leq 10\text{mmHg}$	$\leq 15\text{mmHg}$	Grade 1	Mean	SD
Pass requirement	Two of	73	87	96			
	All of	65	81	93			
Achieved	SBP	360	361	362	363	364	365
	DBP	366	367	368	369	370	371
Part 2		$2/3 \leq 5\text{mmHg}$	$0/3 \leq 5\text{mmHg}$	Grade 2	Grade 3		
Pass requirement		≥ 24	≤ 3				
Achieved	SBP	372	373	374	375		
	DBP	376	377	378	379		
Part 3		Result					
		380					

In order for the device to pass, all protocol requirements must be fulfilled. A fail in any part will result in an overall fail

Box 360: Enter the number of SBP differences (at most 99) between observer and device measurements falling within 5 mmHg.
(The total number of *Boxes* 273, 275 and 277 circled A in the 33 subjects)

Box 361: Enter the number of SBP differences (at most 99) between observer and device measurements falling within 10 mmHg.
(The total number of *Boxes* 273, 275 and 277 circled A or B in the 33 subjects)

Box 362: Enter the number of SBP differences (at most 99) between observer and device measurements falling within 15 mmHg.
(The total number of *Boxes* 273, 275 and 277 circled A, B or C in the 33 subjects)

Box 363: If Boxes 360, 361 and 362 fulfil the Pass requirements, then this is 'Pass'; otherwise, it is 'Fail'.

Boxes 364–365: Enter the mean and standard deviation respectively of the 99 SBP differences between observer and device measurements. (Use data from circled *Boxes* 261 or 267, 263 or 269 and 265 or 271)

Box 366: Enter the number of DBP differences (at most 99) between observer and device measurements falling within 5 mmHg.
(The total number of *Boxes* 274, 276 and 278 circled A in the 33 subjects)

Box 367: Enter the number of DBP differences (at most 99) between observer and device measurements falling within 10 mmHg.
(The total number of *Boxes* 274, 276 and 278 circled A or B in the 33 subjects)

Box 368: Enter the number of DBP differences (at most 99) between observer and device measurements falling within 15 mmHg.
(The total number of *Boxes* 274, 276 and 278 circled A, B or C in the 33 subjects)

Box 369: If Boxes 366, 367 and 368 fulfil the Pass requirements, then this is 'Pass'; otherwise, it is 'Fail'.

Boxes 370–371: Enter the mean and standard deviation respectively of the 99 DBP differences between observer and device measurements. (Use data from circled *Boxes* 262 or 268, 264 or 270 and 266 or 272)

Box 372: Enter the number of subjects (at most 33) with two or three of the absolute differences between observer and device SBP measurements within 5 mmHg. (*Box* 279 is 2 or 3)

Box 373: Enter the number of subjects (at most 33) with none of the absolute differences between observer and device SBP measurements within 5 mmHg. (*Box* 279 is 0)

Box 374: If Boxes 372 and 373 fulfil the Pass requirements, then this is 'Pass'; otherwise, it is 'Fail'.

Box 375: If Boxes 363 and 374 are both 'Pass', then this is 'Pass'; otherwise, it is 'Fail'.

Box 376: Enter the number of subjects (at most 33) with two or three of the absolute differences between observer and device DBP measurements within 5 mmHg. (*Box* 280 is 2 or 3)

Box 377: Enter the number of subjects (at most 33) with none of the absolute differences between observer and device DBP measurements within 5 mmHg. (*Box* 280 is 0)

Box 378: If Boxes 376 and 377 fulfil the Pass requirements, then this is 'Pass'; otherwise, it is 'Fail'.

Box 379: If Boxes 369 and 378 are both 'Pass', then this is 'Pass'; otherwise, it is 'Fail'.

Box 380: If Boxes 375 and 379 are both 'Pass', then this is 'Pass'; otherwise, it is 'Fail'.

In validations carried out in specific populations requiring more than 33 subjects, proportionally equivalent passing criteria should be used.

